# **10.0** Data Management

For Aim 1, we will use non-inferiority analysis methods (margin=0.10) to determine whether simpler control methods are as effective as the most complex control method at shaping foot placement. Based on our preliminary data, a power analysis found that a sample size of 12 would be sufficient for a power of over 90%.

For Aim 2, we will use a two-way repeated measures ANOVA with interactions to determine whether changes in our metric of the typical gait stabilization strategy is significantly influenced by assessment session number or group (Error-Reduction vs. Error-Augmentation vs. Control). Based on our preliminary data, a power analysis found

that a sample size of 14 per group (accounting for 4 dropouts) would be sufficient for a power of over 80%.

The analyses in Aim 3 are more exploratory. We will use multivariate linear regression analyses to determine whether baseline measures of participant function can predict whether an individual at a given functional level is more likely to benefit from Error-Reduction or Error-Augmentation methods.

Steps will be taken to minimize the risk of loss of confidentiality. Clinical data from assessment sessions will be recorded on hard copies (stored in a locked file cabinet in a locked office) and entered into an electronic spreadsheet by the physical therapist immediately after each session. Gait and strength data will be analyzed using a custom MATLAB program, automatically populating a spreadsheet. The research assistant will check the data entry, and pool all data into a group-wide de-identified spreadsheet. All data from training sessions will also be analyzed and stored using an automated MATLAB program. All electronic data will be stored on a password-protected secure server that is backed-up nightly. Upon completion of Aim 2, the de-identified spreadsheets and group assignment list will be shared with the statistician for analysis. The de-identified dataset will be available for sharing with other investigators, and this trial will be registered in the NIH-supported registry.

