## 1.0 Objectives / Specific Aims

Following a stroke, quality of life is often limited by gait instability [1], due to increases in fall-risk [2-3] and fear of falling [4-5]. Recent large-scale interventions have failed to effectively address this problem [6-8], likely as a result of not being targeted to the mechanisms underlying post-stroke gait instability. This project will conduct initial testing of a novel rehabilitation method designed to improve post-stroke gait stability, based on mechanistic principles of motor learning. Specifically, this work is based on our promising preliminary work, in which weak mediolateral forces applied to the legs during walking using a novel force-field caused beneficial stabilizing after-effects in both neurologically intact controls and individuals who had experienced a stroke.

The first Aim is to identify the simplest force-field control method sufficient to modulate foot placement. We hypothesize that adjusting foot placement based solely on pelvis displacement will be sufficient to produce a more stable gait pattern. The second Aim (the clinical trial component) is to determine whether repeated gait practice with foot placement error-reduction or error-augmentation methods promotes retained use of the typical gait stabilization strategy. We hypothesize that error-augmentation methods will produce significantly larger effects than observed in either an error-reduction group or a control group. The third Aim is to quantify the effects of baseline characteristics and intervention dosage on the responses to error-reduction and error-augmentation methods. We hypothesize that lower-functioning individuals will benefit more from error-reduction, while higher-functioning individuals will benefit more from error-augmentation.

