#### 3.0 Intervention to be studied

Aim 2 of this study will involve the initial testing of an entirely novel intervention, to determine whether larger-scale testing is justified. Given the novelty of this intervention, no citations are available. However, the structure of this intervention is directly based on a well-known intervention (split-belt walking) that has the similar goal of improving the characteristics of walking among chronic stroke survivors [20].

No medications are involved in this intervention.

A novel mechanical device is involved in this intervention. Specifically, we have developed a force-field that is able to apply weak mediolateral forces to the legs of users while they walk. The device consists of linear actuators (i.e. motors) that are used to reposition trolleys within steel frames that are secured in front and behind a treadmill embedded in the floor of the laboratory. Nylon-coated wires in series with extension springs run from the trolley behind the treadmill to the trolley in front of the treadmill, always running parallel to the walking direction. These wires pass through leg cuffs strapped to the lateral sides of the users' legs, with an orientation that allows completely

free motion of the legs in the anteroposterior (forward/backward) and vertical directions. The only effect of the wires is to exert a weak mediolateral force on the legs when they deviate from the mediolateral position of the corresponding actuators.

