The intervention will include 54 chronic stroke survivors, divided into three groups: 1) an Error-Reduction group; 2) an Error-Augmentation group; 3) an Activity-Matched Control group. The intervention will include 24 training sessions over a 12-week period. Assessment sessions will be performed prior to beginning the intervention, every 4-weeks during the intervention, and at a 12-week follow-up. Details of the procedures are described below under Study Design / Methods.

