## 11.0 Provisions to Monitor the Data to Ensure the Safety of Subjects

A Data Safety Monitoring Board (DSMB) will oversee the experiments in Aim 2 (a small-scale randomized controlled trial). This board will consist of [name] (a physical therapist and principal investigator of the TIGRR program for promoting rehabilitation research), [name] (a neurologist and stroke-recovery researcher at MUSC), and [name] (a PhD level biostatistician). The DSMB will meet on a quarterly basis. The role of the DSMB will be to:

- Protect the safety of study participants
- Review the research protocol, informed consent documents, amendments, and plans for data safety and monitoring
- Evaluate the progress of the trial, including periodic assessments of data quality and timeliness, recruitment, accrual, and retention, participant risk vs. benefit, and other factors that may potentially affect study outcome
- Review study performance, make recommendations and assist in the resolution of problems reported by the Principal Investigator
- Report to the IRB on the safety and progress of the trial
- Ensure the confidentiality of the study data and the results of the monitoring
- Advise the IRB and the study investigators as to whether the protocol should continue as scheduled or undergo a modification due to a finding from the monitoring process

Any adverse events will be recorded, monitored, and promptly reported to the IRB, following policy HRPP 4.7. Our exclusion criteria will minimize the risk of enrolling participants with severe cardiovascular risk. Scheduled rest breaks will be provided between trials during experimental testing, as well as whenever requested. Minimization of

risk of adverse events will be accomplished by monitoring vital signs during trials in which subjects are performing potentially demanding exercise.

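### Aim 2 names only a session-by-group repeated-measures ANOVA, with no analysis population, missed-visit rule or baseline covariate; a baseline-adjusted mixed model on all randomised participants would be a cheap, modest improvement

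*Combined protocol and SAP*

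**What the plan says.** Section 10.0 (Data Management) gives Aim 2 one analysis sentence. It states that "we will use a two-way repeated measures ANOVA with interactions to determine whether changes in our metric" are "significantly influenced by assessment session number or group (Error-Reduction vs. Error-Augmentation vs. Control". No other Aim 2 model is named and no baseline covariate is listed. It is also unclear whether baseline is one level of the session factor or is subtracted beforehand.

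The next sentence bases power on "a sample size of 14 per group (accounting for 4 dropouts", against 18 enrolled per group in Section 9.0. This is the only mention of dropout. The remaining Aim 2 analysis step is a hand-over: "Upon completion of Aim 2, the de-identified spreadsheets and group assignment list will be shared with the statistician for analysis".

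Section 3.0 sets the schedule: "Assessment sessions will be performed prior to beginning the intervention, every 4-weeks during the intervention, and at a 12-week follow-up". Counting weeks 4, 8 and 12, that is five assessments per person. Section 8.0 adds that participants are reminded at every session that they may stop.

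Section 11.0 calls Aim 2 "a small-scale randomized controlled trial", while Section 9.0 says only that participants are assigned to groups. No section defines an analysis population or a rule for missed assessments.

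**The concern.** The usual complete-case fit of a repeated-measures ANOVA needs every session from every participant. If that fit is used, a participant who attends four of five assessments contributes nothing, and the comparison is no longer of everyone randomised. Because no rule is written, the choice falls to whoever runs the analysis, possibly after the data and group list have been seen.

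The stakes are moderate. Aim 2 is meant "to determine whether larger-scale testing is justified", and its question is whether practice "promotes retained use of the typical gait stabilization strategy". That puts weight on the late assessments, which dropouts are most likely to miss. With 14-18 per group, discarded data and an unused baseline value both cost precision. If people leave because of how they are progressing, and do so differently by group, completers are no longer comparable between groups.

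**Working it through.** **The plan's own figure.** 18 - 4 = 14 per group; 4/18 = 22.2%; over three groups, 12 of 54 leave and 42 complete. The dropout step is consistent. The power figure (over 80%) cannot be reproduced, because the protocol gives no effect size, SD, correlation, alpha or sidedness.

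**Data a complete-case fit would leave unused.** Completers supply 42 x 5 = 210 assessments. The 12 dropouts supply, in addition:
- baseline only: 12 of 222 (5.4%)
- baseline and week 4: 24 of 234 (10.3%)
- everything to week 12: 48 of 258 (18.6%)

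**Precision.** Assumptions: raw SD 1 at every session; equal correlation ρ of 0.5 or 0.7 between sessions; two groups of 18 with 4 dropouts each, last seen at week 4, 8 or 12 with equal chance; covariance treated as known.
- Completers, change score: SE = √[2 x 2(1-ρ)/14] = 0.378 / 0.293.
- Completers, baseline-adjusted: SE = √[2(1-ρ²)/14] = 0.327 / 0.270, a reduction of 13.4% / 7.8%.
- Rows using partial data: generalised least squares on all observed sessions.

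| Analysis | Week 12, ρ=0.5 / 0.7 | Follow-up, ρ=0.5 / 0.7 |
|---|---|---|
| Completers, change score | 0.378 / 0.293 | 0.378 / 0.293 |
| Partial data kept | 0.352 / 0.273 (7.0% / 6.8% less) | 0.362 / 0.281 (4.2% / 4.0% less) |
| Completers, baseline-adjusted | 0.327 / 0.270 | 0.327 / 0.270 |
| Both | 0.309 / 0.254 | 0.321 / 0.263 |

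Once baseline is used, partial data add 5.5% / 5.9% at week 12 and 1.8% / 2.7% at follow-up. Dropouts with only a baseline value add 2.8% / 1.7% without baseline adjustment and nothing with it.

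**Check on the baseline gain.** The equal-SD assumption is doubtful, because Section 9.0 admits only people who lack the strategy, judged on this same metric. As an illustration, assume a normal metric, the screening value used as baseline, and the lowest 12 + 54 = 66 of 141 screened entering (47%). The baseline variance falls from 1 to 0.346. The change-score variance becomes (1-ρ)² x 0.346 + (1-ρ²) = 0.837 / 0.541, against 0.75 / 0.51 after baseline adjustment. The SE gain is then 1 - √(0.75/0.837) = 5.3% and 1 - √(0.51/0.541) = 2.9%.

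**Bias, by simulation under assumed mechanisms.** With 22% dropout in one arm only, log-odds 1-1.5 per SD, equal correlation and no true effect, the completer bias is:
- 0.00 SD if dropout depends on the week-4 level
- 0.08-0.13 SD if it depends on the week-4 change
- 0.08-0.19 SD if it depends on the most recent change

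A likelihood model is within 0.002 SD in all three. If correlations decay over time (first-order autoregressive, 0.7-0.9) and dropout depends on level, completer bias is -0.02 to -0.14 SD, so the sign is not known in advance. A second simulation had 18 per group, a true effect of 1.0 SD and the poorest early responders leaving one arm. Completer bias was 0.16, 0.11 and 0.05 SD at ρ = 0.5, 0.7 and 0.9, and at most about 0.01 SD using everyone. Under completely random dropout, both methods were within about 0.01 SD.

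If dropout depends on the unseen final change, the model helps only in part: bias at follow-up falls from 0.16-0.27 to 0.11-0.19 SD.

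**The case against.** The strongest reply is that the harm is inferred rather than written in the plan. Section 10.0 names a factor structure, not an estimator, and a mixed model can fit session, group and their interaction. The protocol nowhere says that dropouts are removed. This stands: the loss of data is conditional on a complete-case fit.

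A reader might go on to infer that the trial is underpowered. The documents do not support that. Enrolling 18 and powering on 14 already covers the planned dropouts. Power falls below plan only if further people miss isolated visits. For illustration, 2-5% missed per post-baseline visit among the other 42 would leave 12.9-11.4 per group and turn 80% pairwise power into about 76-71%. That miss rate is assumed, the plan claims more than 80%, and a pairwise t-test is not the planned test.

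A reader might also infer that the comparison will be biased or its error rate inflated. Nothing in the documents suggests differential dropout; the allowance is the same 4 in each group. If a 0.19 SD bias did arise from one-arm dropout (14 v 18), a 5% pairwise test would reject about 8.1% of the time. That is a scenario, not a forecast.

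It is also fair that the gain from partial data is small at follow-up, that selection on the metric shrinks the baseline gain, that this is a small first test of a device, and that a mixed model is not the only sound remedy. What survives is that the population and missed-visit rule are absent, and that a more efficient and robust analysis costs almost nothing to write down.

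**Conclusion.** The point holds as a worthwhile improvement in precision and robustness, not as a demonstrated error. The protocol expects 22% dropout over five assessments and states no analysis population, missed-visit rule or baseline adjustment.

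Under the assumed correlations and dropout times, keeping partial data is worth about 7% of the standard error at week 12 and 4% at follow-up, or about 6% and 2-3% once baseline is used. Baseline adjustment is worth up to 8-13% with equal SDs and perhaps 3-5% if selection narrows the baseline spread. Protection against bias has value only if dropout is related to observed progress and differs by group; neither its presence nor its sign can be read from the documents. Every size given here rests on assumed values, because the protocol gives no SD, correlation or effect size.

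**What to change.** Before the group list goes to the statistician, replace the Aim 2 ANOVA sentence in Section 10.0 with a paragraph that specifies:
- **Population:** all randomised participants, in their assigned group, with all available assessments.
- **Model:** a likelihood-based linear mixed model for repeated measures with group, categorical session, group-by-session and baseline. Baseline enters either as a covariate or through group means constrained equal at baseline.
- **Small sample:** a degrees-of-freedom correction, and a named simpler covariance structure if the first does not converge.
- **Missing data:** a statement that the model is valid under missing at random, and a simple sensitivity analysis for missing not at random, for example shifting the unobserved values of dropouts by a range of amounts in each group.
- **Supplement:** the completer ANOVA, reported alongside.

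The cost is one paragraph and a little more analysis work, with no extra participants, visits or change to conduct. There are two downsides. The covariance fallback may be needed with groups this small, and the model corrects only part of the bias if dropout depends on values that were never observed.

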# 9.0 Study Design / Methods

This study will consist of three Aims. Before enrollment in any of the experiments, we will first determine whether potential participants lack the typical gait stabilization strategy (the focus of this project). This will be accomplished in an initial assessment session, described in more detail below. Briefly, we will determine if each participant adjusts their mediolateral foot placement based on the mechanical state of their pelvis. We anticipate that up to a total of 141 chronic stroke survivors will be enrolled in this initial assessment session.

All assessment sessions in this study will last approximately 3 hours, and will involve the quantification of several metrics:

• Biomechanical gait characteristics. Participants will walk on an instrumented treadmill (Bertec; Columbus, OH) at their self-selected speed for 3-minutes. Active LED markers (PhaseSpace; San Leandro, CA) will be placed on participants' legs. This equipment will allow us to quantify gait kinetics and kinematics. Of primary interest, we will use these data to quantify the correlation between pelvis mechanics at the start of a step and step width at the end of a step, our primary measure of whether an individual is using the typical gait stabilization strategy.

- Self-selected overground gait speed. Participants will perform 5 trials walking along a 10-meter straight line path at their self-selected speed, with 2 unrecorded meters for both acceleration and deceleration.
- Clinical tests. A blinded physical therapist will quantify several measures of
  post-stroke function commonly used clinically (e.g. Functional Gait
  Assessment; Activities-specific Balance Confidence scale; Fear of Falling; Fall
  incidence; Fugl-Meyer Lower Extremity Motor Function subscale; Fugl-Meyer
  Sensation subscale).

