The first 12 participants from the initial assessment session who do not use the typical gait stabilization strategy will be enrolled in Aim 1. This Aim consists of a single experimental session, which will last approximately 3 hours. Participants will perform a series of treadmill trials at their self-selected speed, in which our novel force-field will produce varied assistive patterns of force. Specifically, the assisted foot placement will be based on various combinations of pelvis displacement, pelvis velocity, and average step width. As in assessment sessions, active LED markers will be placed on participants' legs, allowing us to quantify biomechanical gait characteristics.

The next 54 participants from the initial assessment session who do not use the typical gait stabilization strategy will be enrolled in Aim 2. Of note, participants from Aim 1 will be eligible to re-enroll after a 4-week washout period. Participants will be assigned to either an Error-Reduction group (n=18), an Error-Augmentation group (n=18), or an Activity-Matched Control group (n=18). Each of these groups will complete a 12-week (24-training session) intervention. Assessment sessions will be performed every 4-weeks during the intervention, and as a 12-week follow-up.

For each training session (lasting ~1 hour), participants will perform a series of walking trials at their self-selected speed, both overground and on a treadmill. This will include ten 3-minute trials in which participants are interfaced with the force-field. The force-field will be programmed to either assist foot placement (Error-Reduction), perturb foot placement (Error-Augmentation), or simply get out of the way (Control). As in assessment sessions, active LED markers will be placed on participants' legs, allowing us to quantify biomechanical gait characteristics.

Aim 3 involves only secondary analyses of data collected in the experiments for Aim 2.

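### Aim 2 analyses changes without adjusting for the pre-training value of the metric; adjusting is a cheap option that would modestly sharpen the group contrasts

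*Combined protocol and SAP*

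**What the plan says.** Section 10.0 (Data Management) gives the Aim 2 analysis in one sentence. The model is a "two-way repeated measures ANOVA with interactions". The question put to it is if "changes in our metric of the typical gait stabilization strategy is significantly influenced by assessment session number or group". The groups are error-reduction, error-augmentation and control. No covariate is named there or elsewhere for this test. Baseline measures of function enter only the exploratory Aim 3 regression.

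The pre-training value is available. Section 3.0 states: "Assessment sessions will be performed prior to beginning the intervention, every 4-weeks during the intervention, and at a 12-week follow-up". Section 9.0 says that every assessment session will "quantify the correlation between pelvis mechanics at the start of a step and step width at the end of a step", which is the primary measure.

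The Aim 2 hypothesis in section 1.0 is a pair of group contrasts: "error-augmentation methods will produce significantly larger effects than observed in either an error-reduction group or a control group". Section 9.0 assigns 18 people to each group, and section 10.0 states that "a sample size of 14 per group (accounting for 4 dropouts) would be sufficient for a power of over 80" per cent. Entry depends on the same metric: only those "who do not use the typical gait stabilization strategy will be enrolled in Aim 2".

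**The concern.** Subtracting baseline is not the same as adjusting for it. A change score sets the slope of the later value on the baseline value to 1. If the true slope is lower, a chance difference in baseline between two arms leaves (1 − slope) times that difference in the group contrast, and the contrast carries extra variance. With 14 completers per arm such differences are not rare: the SE of a baseline difference is √(2/14) = 0.378 SD, so a given pair of arms differs by more than 0.5 SD in about 19% of randomizations. At stake is some precision in the contrasts that the Aim 2 hypothesis is about, in a small trial where the covariate costs nothing to collect.

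**Working it through.** **The plan's own figure.** The head count checks: 18 − 4 = 14 per group and 3 × 18 = 54. The stated power cannot be reproduced, because section 10.0 gives no effect size, SD, correlation, alpha or tested term. At two-sided 0.05 with 39 error df, 80% power for one pairwise contrast at 14 per group needs a difference of 1.09 SD of the analysed quantity.

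**Assumptions (not in the documents).** Changes are post-baseline minus pre-training values. The baseline SD is 1 before selection, and r is the correlation between visits before selection, from 0.5 to 0.9. Alpha is two-sided 0.05. There are four post-baseline visits (weeks 4, 8 and 12, and follow-up) with equal correlation between them. Two cases are used for selection at entry:

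- *None*: baseline variance Vb = 1.
- *Strong*: the lowest 66 (12 + 54) of the 141 screened are enrolled. A normal distribution cut at 66/141 = 0.468 has Vb = 0.346.

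**Formulas.** The residual variance given baseline, R, is 1 − r² for one visit and (r − r²) + (1 − r)/4 for the mean of four visits. The change-score variance is R + (1 − r)²·Vb. The variance ratio is R divided by that sum.

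Example for r = 0.5, one visit, strong selection: R = 0.75, change-score variance = 0.75 + 0.25 × 0.346 = 0.837, ratio = 0.897.

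Adjusted power uses the noncentral t with 38 df, with the variance multiplied by (1 + 1/37) for average covariate imbalance. The effect is set so that change scores have 80% power.

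| r | Strong, one visit: ratio, power | Strong, four visits | None, one visit | None, four visits |
|---|---|---|---|---|
| 0.5 | 0.897, 83.1% | 0.812, 86.5% | 0.75, 89.1% | 0.60, 94.6% |
| 0.7 | 0.942, 81.2% | 0.901, 82.9% | 0.85, 85.0% | 0.76, 88.7% |
| 0.8 | 0.963, 80.4% | 0.938, 81.4% | 0.90, 82.9% | 0.84, 85.4% |
| 0.9 | 0.982, 79.6% | 0.971, 80.1% | 0.95, 80.9% | 0.92, 82.1% |

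**Cost when there is nothing to gain.** With a true slope of 1 the ratio is 1, and power falls from 80% to 78.9%.

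**Unequal slopes.** Section 1.0 expects that "lower-functioning individuals will benefit more from error-reduction, while higher-functioning individuals will benefit more from error-augmentation", so slopes may differ by arm. Take slopes 0.3, 0.5 and 0.7 (pooled 0.5) and a 0.5 SD baseline gap carried wholly by one arm. Common-slope adjustment leaves 0.5 × |slope − 0.5|, which is 0.10, 0 or 0.10 SD. Change scores leave 0.5 × |slope − 1|, which is 0.35, 0.25 or 0.15 SD.

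**Group-by-session test.** A common-slope covariate shifts all post-baseline values of one person by the same amount, so it cancels from within-person comparisons. In one simulated complete data set the group-by-session F was 0.9287 with and without the covariate, while the group F moved from 3.59 to 6.27. A baseline-by-session term can change the interaction test.

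**The other reading of changes.** Suppose raw values are analysed with the pre-training visit as a session level. The treatment effect then sits in the group-by-session term. In simulation, with the effect sized for 80% power of the change-score group test, that interaction test had about 46 to 59% power if the effect is constant from week 4 and 73 to 87% if it builds up. The adjusted group test had 80 to 95% for the constant effect. Neither approach is always more powerful.

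**The case against.** The strongest reply is that nothing needs repair. Change scores already use baseline, the trial is described as initial testing, and a one-sentence analysis plan that omits a covariate has not ruled one out. That stands, and it is why this is an optional improvement.

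The reply adds that the gain may be negligible. Entry selects on the metric, and with strong selection and one visit the gain is between about +3 and −0.4 points. That also stands. The larger figures need an unrestricted baseline range, which fits the screening step poorly.

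The magnitudes rest wholly on assumptions. The 66 of 141 yield is itself one: section 9.0 lets Aim 1 participants re-enrol, and 141 is an upper limit. Taking the lowest 54 instead hardly changes the results (83 to 80% for one visit, 86 to 80% for four).

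A reader might infer that the planned test is biased or has inflated type I error. It is not, and it does not. Given a 0.5 SD gap and slopes of 0.5 or 0.7, the conditional type I error of change scores is about 5.5 to 7.4%. At zero gap it is 2.4 to 4.4% (one visit), and for gaps below about 0.38 SD, roughly two-thirds of randomizations, it is under 5%. Over all randomizations it is 5%.

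**Conclusion.** The point holds as a low-priority efficiency option, not a flaw. If changes are post-baseline minus pre-training values, adjustment multiplies the error variance of a group contrast by about 0.90 to 0.98 (one visit) or 0.81 to 0.97 (mean of four visits) under strong selection, and by 0.75 to 0.95 or 0.60 to 0.92 with no selection. Adjustment reduces the error from chance imbalance. It removes it fully only if the relation to baseline is linear with a common slope.

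Two further inferences are not supported. The gain cannot be called large, because the documents give no correlation, SD or cut-off and the entry criterion points to the smaller figures. Nor does adding baseline alone sharpen the group-by-session test; the benefit is in the group main effect and the contrasts at each session. If section 10.0 intends raw values with baseline as a session level, the question becomes which term is tested.

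**What to change.** In section 10.0, before the data and group list go to the statistician:

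- State that the post-baseline values (weeks 4, 8 and 12, and follow-up) are analysed in the repeated measures model, with the pre-training value and its interaction with session as covariates. A constrained-baseline longitudinal model is an alternative.
- Name the tested terms: error-augmentation against error-reduction, and error-augmentation against control.
- Plan a check of linearity and of equal slopes across arms, since the metric is a bounded correlation and response is expected to depend on baseline function.

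The cost is a few lines of analysis wording, one to four degrees of freedom, and up to about 1 point of power if the true slope is near 1. No new data, visits or participants are needed.

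### The Aim 2 model has no baseline adjustment and does not say how the pre-intervention value is used; a pre-specified baseline covariate would be a cheap, optional gain in precision

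*Combined protocol and SAP*

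**What the plan says.** Section 10.0 (Data Management) specifies for Aim 2 a "two-way repeated measures ANOVA with interactions to determine whether changes in our metric of the typical gait stabilization strategy" are "significantly influenced by assessment session number or group (Error-Reduction vs. Error-Augmentation vs. Control"). Session, group and their interaction are the only terms. The sample-size statement is that "a sample size of 14 per group (accounting for 4 dropouts) would be sufficient for a power of over 80" per cent; no effect size, SD, alpha or correlation accompanies it.

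Section 9.0 states that "Participants will be assigned to either an Error-Reduction group (n=18), an Error-Augmentation group (n=18") or a control group of the same size, and names no balancing factor. Section 11.0 describes Aim 2 as randomised.

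On timing, section 3.0 says: "Assessment sessions will be performed prior to beginning the intervention, every 4-weeks during the intervention, and at a 12-week follow-up". Under section 9.0 each assessment yields the primary gait metric, clinical function scales and overground gait speed ("Participants will perform 5 trials walking along a 10-meter straight line path at their self-selected speed"). Baseline values of all of these will therefore exist.

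Section 1.0 gives the Aim 2 hypothesis, that "error-augmentation methods will produce significantly larger effects than observed in either an error-reduction group or a control group", and the Aim 3 hypothesis: "We hypothesize that lower-functioning individuals will benefit more from error-reduction, while higher-functioning individuals will benefit more from error-augmentation". Sections 9.0 and 10.0 leave baseline function to Aim 3, which is secondary and labelled exploratory.

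**The concern.** Two things are left open in the main Aim 2 analysis.

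- **The response.** It could be a change score, with the pre-intervention value subtracted. It could also be the metric itself, with the pre-intervention assessment as one session level. The two call for different key tests (a group effect or a group-by-session interaction), and a baseline covariate has to enter differently in each.
- **Baseline information.** The plan measures baseline variables that may explain part of the between-person spread in change, but does not use them in Aim 2. With about 14 completers per arm, any explained variance is worth having.

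What is at stake is precision and readability of the contrasts in a small trial meant to decide whether larger ones are justified. Type I error and bias are not at stake.

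**Working it through.** **Inputs from the documents.** 18 assigned per arm, 4 dropouts, 14 analysed (18 − 4 = 14, consistent), three arms, power over 80%.

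**Assumptions, because the documents are silent.** Power exactly 80%; two-sided alpha 5%; a pairwise t test on one change score with within-arm SD 1 and error pooled over three arms; r (covariate with change) from 0 to 0.5. The stated power cannot be reproduced without an effect size, so the implied effect is back-solved.

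**1. Implied effect.** Error df = 3 × 14 − 3 = 39. Noncentrality = d × √(14/2). Power of 80% needs d = 1.086, so noncentrality = 1.086 × 2.646 = 2.87.

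**2. Power with one common-slope covariate.** Residual variance is multiplied by (1 − r²). Chance imbalance in the covariate costs a factor of about 1 + 1/37 = 1.027. Error df falls to 38. Noncentrality becomes 2.873 / √[(1 − r²) × 1.027].

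| r | variance factor | noncentrality | power, formula | power, simulation |
|---|---|---|---|---|
| 0 | 1.027 | 2.83 | 0.789 | 0.789 |
| 0.17 | 0.997 | 2.88 | 0.801 | 0.800 |
| 0.3 | 0.935 | 2.97 | 0.825 | 0.827 |
| 0.5 | 0.770 | 3.27 | 0.891 | 0.889 |

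The simulation used 200,000 trials per scenario; type I error was 5.0–5.1% throughout. Break-even is at |r| of about 0.17.

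**3. Opposite slopes.** With slopes of −0.5 in Error-Reduction, +0.5 in Error-Augmentation and 0 in Control, the common slope averages about zero. Power is 79% against 80% unadjusted. Slopes of 0.3 give the same result.

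**4. Baseline value of the metric as covariate.** If baseline and later values have equal variance and correlation ρ, then corr(baseline, change) = (ρ − 1)/√(2 − 2ρ) = −√((1 − ρ)/2).

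- ρ = 0.5: −√0.25 = −0.50, so power is about 89%.
- ρ = 0.8: −√0.10 = −0.32, so power is about 83%.
- Break-even: (1 − ρ)/2 = 0.17² = 0.0289, so ρ = 0.94.

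Equal variance is an assumption. In general the correlation is (ρ × SD later − SD baseline)/SD change, which is zero when SD baseline/SD later = ρ. Enrolment is limited to people who lack the typical strategy, which could narrow the baseline spread.

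**5. Where the covariate acts.** In a balanced five-session example with 42 people, a time-constant covariate left the within-person residual sum of squares and its 156 df unchanged, so the group-by-session test did not move. Adding covariate-by-session terms took the df to 152. The adjusted Error-Augmentation versus Control contrast (mean post minus pre) then equalled the change-score ANCOVA contrast.

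**6. Chance imbalance above 0.5 SD on a baseline measure.** For one contrast, the SD of the difference in means is √(2/n).

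- n = 18: 0.5/0.333 = 1.50, two-sided probability 13%.
- n = 14: 0.5/0.378 = 1.32, two-sided probability 19%.
- Any of the three pairs (simulation): 29% and 38%.

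**The case against.** The strongest reply is that the plan is sound as it stands. The comparison is randomised, so it is unbiased without adjustment, and chance imbalance is already in its standard error. The imbalance percentages therefore measure no error. All of this stands. A reader might infer that omitting a covariate invalidates or biases the Aim 2 test; nothing in the documents supports that.

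A second tempting reading is that the Aim 3 hypothesis itself shows that adjusting for gait speed would raise power. It does not. Section 1.0 predicts effect modification, with function favouring different methods at different levels. If the slopes are opposite, a common-slope gait-speed term loses about 1 point. The documents nowhere say that gait speed predicts change in the same direction in every arm, and the predicted interaction already has its place in Aim 3. This objection stands against gait speed as the main covariate. It has less force against the baseline value of the metric, whose link with change is partly arithmetic.

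Third, the power anchor is constructed: section 10.0 says over 80%, for a repeated measures ANOVA. If true power were 90%, the gain at r = 0.3 would be under 2 points (90.0% to 91.8%). This stands, and is why the figures are conditional.

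Stratified assignment might also seem to follow. It would reduce imbalance, but blocks of 3 within two gait-speed strata would leave the arms at 17 to 19 instead of exactly 18 in about 44% of trials. It is a trade-off and not part of this point.

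**Conclusion.** The point holds as an optional improvement in precision, together with a gap in the definition of the response. The gap does not depend on any assumed correlation: section 10.0 does not settle how the pre-intervention assessment enters, and that determines both the key test and where a covariate can act.

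On precision, the range is from a loss of about 1 power point (80% to 79%) to a gain of 9 (80% to 89%) for |r| between 0 and 0.5. This rests on the assumed 80% anchor, two-sided 5% and a difference of 1.09 SD of change. The metric's own baseline is the better-supported covariate, with the equal-variance assumption as the main caveat. Gait speed is a possible addition only.

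**What to change.** Amend section 10.0 before any Aim 2 outcome data are examined. The handover of the assignment list to the statistician is too late a deadline, because that section places it at completion of Aim 2.

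1. State that the response is the metric, or its change from the pre-intervention assessment, at the post-baseline sessions.
2. Include the pre-intervention value of the same metric as a covariate with one common slope. With that covariate in the model, the metric and its change give the same group contrast.
3. If the pre-intervention assessment is instead kept as a session level, enter any time-constant covariate, such as gait speed, with covariate-by-session terms.
4. Baseline gait speed may be named as an optional second covariate. Keep function-by-group terms in Aim 3.

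**Cost.** SAP wording only, since the data are already collected. The covariate uses one model df in the post-baseline form, or four (156 to 152 with five sessions) in the session-level form. The worst case tested costs about 1 power point; a second covariate would use a further df.
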